# 11.3 Exploratory Assessments

### 11.3.1 Growth Parameters

Weight and length/height will be assessed and BMI will be derived. Length/height and weight must be measured with the subject in a dry diaper or dry underclothes only. If the subject is >2 years of age and can stand unassisted and follow directions, standing height should be measured; otherwise recumbent length should be measured. Length should be measured while the subject is supine by measuring from the crown of the head to the bottom of the feet, with the hips and legs straightened. BMI will be calculated using the following equation: BMI (kg/m²) = body weight (kg) ÷ stature² (m²). Z-scores adjusting for age and sex in weight, length/height, and BMI, as well as weight-for-length z-score will be derived. Formulas for calculating z-scores will be provided in the statistical analysis plan (SAP).

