10 STATISTICAL ANALYSIS

10.1 General Considerations

The Schedule of Assessments is provided in the CSP for Study 124. The precision standards for reporting safety and efficacy variables are provided in an internal Biometrics document that specifies the programming rules including the precision for derived variables.

All individual subject data will be presented in data listings based on the All Subjects Set.

Continuous variables will be summarized using the following descriptive summary statistics: number of subjects, mean, standard deviation (SD), standard error (SE), median, minimum value (min), and maximum value (max).

Categorical variables will be summarized using counts and percentages.

Baseline value will be defined as the most recent non-missing measurement (scheduled or unscheduled) collected on or before the first dose of LUM/IVA in Study 124.

For sweat chloride, values at each visit will be based on averaged measurements from left and right arms. For Rollover Subjects, baseline will be defined as the most recent non-missing measurement (scheduled or unscheduled) collected on or before the first dose of LUM/IVA in Study 124. For LUM/IVA-naïve Subjects, baseline will be defined as the average of the values at screening and the pretreatment measurement on Day 1 of Study 124. If only 1 pre-first dose measurement of sweat chloride is available, that measurement will be considered the baseline.

Change (Absolute Change) from baseline will be calculated as postbaseline value – baseline value.

Unscheduled visits will be included in the analysis as follows:

- In scheduled visit windows per specified visit windowing rules
- In the derivation of baseline measurements or last on-treatment visit
- In individual subject data listings, as appropriate
- In the derivation of max/min values and max/min change from baseline values

Visit windowing rules: Appendix defines the visit window mapping rules to derive the analysis visits for Study 124.

Repeated observations within the same visits window:

- For all PD parameters, if there are multiple measurements within a visit window, the record at the scheduled visit will be used. If there are no measurements at the scheduled visit, then 1) the record closest to the target day will be used; or 2) if there are multiple records with the same distance to the target day, the latest record will be used.

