10.5 Exploratory Endpoint Analysis

10.5.1 Absolute Change from Baseline in Growth Parameters

Absolute Change from Baseline in BMI-for-Age Z-score and BMI

BMI z-score will be calculated by using WHO BMI-for-age charts. The BMI-for-age z-score will be calculated as follows:

$$z = \begin{cases} \frac{\left(\frac{X}{M}\right)^{L} - 1}{LS} &, L \neq 0 \\ \frac{\ln\left(\frac{X}{M}\right)}{S} &, L = 0 \end{cases}$$

Where X is the derived BMI value in kg/m² based on the raw weight and raw height and L, M, and S are selected from the WHO BMI-for-age charts by subject sex and age. The BMI-for-AGE z-score tables contain these parameters by sex and age; they are available at (accessed Jun 09, 2023):

https://www.who.int/toolkits/child-growth-standards/standards/body-mass-index-for-age-bmi-for-age

Raw values and absolute change from baseline in BMI and BMI-for-age z-score at each visit will be summarized descriptively (n, mean, SD, SE, median, minimum, and maximum) based on the FAS. In addition, the 95% CI of the absolute change from baseline values will be provided. The mean (95% CI) of the absolute change from baseline values will be plotted at each scheduled visit.

Absolute Change from Baseline in Weight-for-Age Z-score and Weight

Weight-for-age z-score will be calculated by using WHO weight-for-age tables. The same equation used to calculate BMI-for-age z-score will be used to calculate weight-for-age z-score, where X in the equation will be the collected weight. L, M, and S parameters will be selected from the WHO weight-for-age tables. The weight-for-age z-score tables contain these parameters by sex and age; they are available at (accessed Jun 09, 2023):

• https://www.who.int/tools/child-growth-standards/standards/weight-for-age Weight-for-age z-score and weight will be analyzed in a similar way to BMI-for-age z-score and BMI.

Absolute Change from Baseline in Length/Height-for-Age Z-score and Length/Height

Length-for-age z-score will be calculated by using WHO length-for-age tables. The same equation used to calculate BMI-for-age z-score will be used to calculate length-for-age z-score, however X in the equation will be the collected length. L, M, and S parameters will be selected from the WHO length -for-age tables. The length-for-age z-score tables contain these parameters by sex and age; they are available at (accessed Jun 09, 2023):

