• https://www.who.int/tools/child-growth-standards/standards/length-height-for-age See Appendix G Computing Z-Scores Using WHO Standards for further details on determining length/height and necessary adjustment.

Length/height-for-age z-score and length/height will be analyzed in a similar way to BMI-for-age z-score and BMI.

Absolute Change from Baseline in Weight-for-Length Z-Score

Weight-for-length z-score will be calculated by using WHO weight-for-length tables. The same equation used to calculate BMI-for-age z-score will be used to calculate weight-for-length z-score, where X in the equation will be the collected weight. L, M, and S parameters will be selected from the WHO weight-for-length/height tables. The weight-for-length z-score tables contain these parameters by sex and length/height; they are available at (accessed Jun 09, 2023):

• https://www.who.int/tools/child-growth-standards/standards/weight-for-length-height

See Appendix G Computing Z-Scores Using WHO Standards for further details on determining length/height and necessary adjustment.

Weight-for-length z-score will be analyzed in a similar way to BMI-for-age z-score.

10.5.2 Absolute Change from Baseline in Markers of Pancreatic Function Absolute Change from Baseline in FE-1 Levels

Raw values and absolute change from baseline in FE-1 levels at each visit will be summarized descriptively (n, mean, SD, SE, median, minimum, and maximum) based on the FAS. In addition, the 95% CI of the absolute change from baseline values will be provided.

In addition, the number and percentage of subjects with FE-1 levels consistent with pancreatic insufficiency (defined as FE-1 level <200 mg/kg) will be provided at baseline and at each visit.

The number and percentage of subjects with shift changes from baseline at each visit will be summarized using the following two categories: <200 mg/kg; ≥200 mg/kg.

The mean (95% CI) of the absolute change from baseline in FE-1 values will be plotted at each scheduled visit.

Absolute Change from Baseline in Serum IRT Levels

Raw values and absolute change from baseline in serum IRT levels at each visit will be summarized descriptively (n, mean, SD, SE, median, minimum, and maximum) based on the FAS. In addition, the 95% CI of the absolute change from baseline values will be provided.

The mean (95% CI) of the absolute change from baseline in serum IRT values will be plotted at each scheduled visit.

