10.6.4 Vital Signs

For vital signs measurements, raw values and change from baseline values will be summarized at each visit of the TE Period for the following parameters: systolic and diastolic blood pressure (SBP/DBP) (mmHg), temperature (°C), pulse rate (beats per minute), respiratory rate (breaths per minute), weight (kg), length/height (cm), and BMI (kg/m²).

The number and percentage of subjects with at least one potentially abnormal SBP and/or DBP during the TE Period of the TE Period will be summarized separately based on the Safety Set using threshold criteria provided in Appendix. Potentially abnormal SBP and DBP by percentile (adjusted for sex, age, and length/height) will be provided, including:

- Number and percentage of subjects in categories: $\geq 90\%$ to < 95%; $\geq 95\%$ to < 99% + 5 mmHg; $\geq 99\% + 5$ mmHg, during the TE Period
- Number and percentage of subjects with SBP and DBP percentiles ≥95% at least once and at least twice during the TE Period
- Number and percentage of subjects with SBP and DBP percentiles ≥95% at each visit in the TE Period

The length/height adjustment will be based on length/height-for-age z-scores and their corresponding percentiles using the standard normal distribution (Appendix). The length/height percentiles will be further mapped per the following rules displayed in Table 9-1:

Table 9-1 Grouped Percentiles for Length/Height-for-Age Z-scores

Calculated Percentiles (%)	Grouped Percentiles (%)

0 – <7.5	5
7.5 – <17.5	10
17.5 – <37.5	25
37.5 – <62.5	50
62.5 – <82.5	75
82.5 – <92.5	90
92.5 – 100	95

The sex- and age-adjusted normal range for SBP and DBP for each grouped length/height percentile is based on the SBP/DBP table on the National Heart, Lung, and Blood Institute (NHLBI) website (http://www.nhlbi.nih.gov/health-pro/guidelines/current/hypertension-pediatric-jnc-4/blood-pressure-tables, accessed Oct 26, 2021).

Listings of subjects with potentially abnormal SBP and/or DBP will be provided.

The mean (+/- SD) value at each visit will be plotted separately for SBP and DBP.

Listings will be provided for vital signs parameters.

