Appendix G Computing Z-Scores Using WHO Standards

Adjusting Length/Height for Recumbent vs. Standing Position

In calculation of z-scores relating to length/height, an adjustment may be necessary depending on how the length/height data were collected and the child's age (World Health Organization, 2006; Schumacher, 2020).

If the Measures are KNOWN to Be Either Recumbent Length or Standing Height:

- If the subject's age is ≤ 24 Months (730 days), measure of recumbent length should be used. If standing height measure is collected instead, **0.7 cm must be ADDED** to the standing height measure to adjust.
- If the subject's age is > 24 Months (730 days), measure of standing height should be used. If recumbent length measure is collected instead, **0.7 cm must be SUBTRACTED** from the recumbent length measure to adjust.

If the Measures are **UNSPECIFIED** to Be Either Recumbent Length or Standing Height:

- If AGE at the Visit is Not Missing
 - o If child age is \leq 24 Months (730 days), the measure is to be considered as recumbent length
 - o If child age is > 24 Months (730 days), the measure is to be considered as standing height
- If Age at the Visit is Missing
 - o If the measure is < 87cm, it is to be considered as recumbent length
 - o If the measure is ≥ 87 cm, it is to be considered as standing height

If necessary, all ages collected in months can be converted to days using 1 month = 30.4375 days.

Linear Interpolation of Length/Height Measurements

The WHO standard tables for Weight-for-Length/ Height comes with tabulated Length/Height (X) values with 1 decimal place and at 0.1 intervals. In practice, if the collected Length/Height (X) values fall between the intervals, the following interpolation approach is suggested to obtain the appropriate values for L, M, and S (World Health Organization, 2006):

- 1. Round the **Length/Height** (X) to the nearest 1 decimal place value lower than the collected value (e.g., round 73.265 to 73.2), and obtain the L, M, and S values using the standard table. Let us denote the rounded value as (X_l) and the tabulated values as L_l , M_l , and S_l .
- 2. Round the **Length/Height** to the nearest 1 decimal place value higher than the collected value (e.g., round 73.265 to 73.3), and obtain the *L*, *M*, and *S* values using

the standard table. Let us denote the rounded value as (X_u) and the tabulated values as L_u , M_u , and S_u .

3. Obtain the interpolated values of L, M, and S as:

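### Change from baseline in raw length/height and raw BMI mixes recumbent and standing measurements: each child who switches has growth understated by 0.7 cm and BMI change raised by about 0.2 to 0.3 kg/m² (stature and BMI assumed)

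*SAP*

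**What the plan says.** **Endpoints.** SAP 10.5.1 states: "Raw values and absolute change from baseline in BMI and BMI-for-age z-score at each visit will be summarized descriptively", with a 95% CI and a plot of the mean change by visit. It adds: "Length/height-for-age z-score and length/height will be analyzed in a similar way" to BMI. SAP 10.6.4 repeats raw values and change for "length/height (cm), and BMI" as vital signs. Protocol 12.3.4.1 and 12.3.5.4 also call for raw values and change.

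**Definition of change.** Under SAP 10.1, change "from baseline will be calculated as postbaseline value" minus baseline value. Nothing requires the two values to come from the same measuring position.

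**Measuring position.** Protocol 11.3.1 says that for a child over 2 who can stand alone and cooperate, "standing height should be measured; otherwise recumbent length should be measured". BMI is weight over measured stature squared. Protocol 11.4.4 lets a child stay recumbent past age 2 until comfortable with standing measurement.

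**Appendix G.** Its scope is z-scores: "In calculation of z-scores relating to length/height, an adjustment may be necessary". At 24 months or younger it expects recumbent length and adds 0.7 cm to a standing measure. Above 24 months, "measure of standing height should be used. If recumbent length measure is collected instead", 0.7 cm is subtracted. Where position is unspecified and the child is over 24 months, "the measure is to be considered as standing height".

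**The concern.** A child measured lying down at baseline and standing at a later visit has two statures on different scales. The SAP itself puts the gap at 0.7 cm. Subtracting one from the other builds the gap into the change: apparent growth is too small and, because BMI divides by stature squared, apparent BMI gain is too large.

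The error runs in one direction, so the 95% CI does not reflect it. It can also enter progressively as children move to standing measurement, which would alter the shape of the plotted curves. Raw BMI is the more exposed measure: its true change may be close to zero, whereas raw length change in toddlers is mostly growth of many centimetres.

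**Working it through.** The plan gives no figure on this point, so there is nothing to reproduce. Inputs from the documents are the 0.7 cm constant and 30.4375 days per month (SAP Appendix G), naïve age of 12 to <24 months on Day 1 (Protocol 8.2.1), and 96 weeks of treatment (Protocol 9.1.2). Stature and BMI values are assumptions.

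1. **Length/height.** Let Lb and Lf be true recumbent lengths at baseline and follow-up. Reported change = (Lf − 0.7) − Lb = true change − 0.7 cm. Example: Lb = 78 and Lf = 94 give 93.3 − 78 = 15.3 cm, against 16.0 cm in one position.

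2. **Appendix G applied to raw values.** Recumbent at ≤24 months: adjustment 0. Standing at >24 months: adjustment 0. The 0.7 cm step remains, because the appendix moves only measurements that are out of position for age.

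3. **BMI.** Offset = BMI × [(L/(L − 0.7))² − 1], with L the recumbent length in cm.
   - Against a recumbent basis (follow-up L assumed 85–95 cm): BMI 15, L 95: 0.224. BMI 16, L 85/90/95: 0.267/0.252/0.238. BMI 17, L 85: 0.283.
   - Against a standing basis (baseline L assumed 72–87 cm): BMI 15, L 87: 0.244. BMI 16, L 72/80/87: 0.316/0.284/0.261. BMI 17, L 72: 0.335.
   - In the example of step 1, an unchanged BMI of 16 would be reported as a rise of 0.24 kg/m².

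4. **Who can switch.** 96 weeks = 672/30.4375 = 22.1 months, so naïve completers are 34.1 to <46.1 months old at Week 96 and all pass 24 months on study. Rollovers have had 24 weeks (5.5 months) in Study 122B, so they are at least 17.5 to 29.5 months old at Day 1. Some are past 24 months by then, but a rollover of that age who is still recumbent at Day 1 can also switch later.

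5. **Visit mean.** Shift = p × 0.7 cm, with p the share switched. At p = 0.5 this is 0.35 cm and, at L 90 and BMI 16, 0.5 × 0.252 = 0.13 kg/m². At p = 1 it is 0.7 cm and 0.25 kg/m². The documents do not give p.

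6. **Scenarios for p, not limits.** Suppose every naïve child stands from 24 months.
   - Ages uniform over 12–24 months: 2.76/12 = 23% past 24 months at Week 12 and 5.52/12 = 46% at Week 24 (0.16 and 0.32 cm).
   - Ages uniform over 18–24 months, since Protocol 9.1 has that group enrolling first: 2.76/6 = 46% and 5.52/6 = 92% (0.32 and 0.64 cm), twice as large.
   - Rollovers, ages at 122B start uniform over 12–24 months and Day 1 after 24 weeks: standing from exactly 24 months gives (12 − 5.52)/12 = 54% (0.38 cm). Standing from 30 months would allow all of them to switch (0.70 cm).

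**The case against.** **Little depends on these summaries.** They are exploratory and descriptive, with no hypothesis test, in an uncontrolled study of growing children. In the example, 0.7 cm is about 4% of a 16.0 cm change. Each raw measure has a paired z-score. This stands, and it is why the point is minor. It does not remove a known one-directional shift from outputs that carry CIs and plots.

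**The protocol itself specifies raw change.** Protocol 12.3.4.1 asks for raw values and absolute change, so replacing that change with an adjusted one would depart from it. This stands; an adjusted analysis should be an addition.

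**Adjustment can miscorrect.** If position is not recorded, Appendix G's age default treats a child over 24 months who is still lying down as standing. Adding 0.7 cm then overstates growth by 0.7 cm and understates BMI change by about 0.2 to 0.3 kg/m². This stands too, so the main adjusted analysis should use recorded position.

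**Stronger readings a reader might infer.**
- That the z-scores are biased as well. The routine switch does not bias them when Appendix G is followed, because recumbent up to 24 months and standing afterwards are the positions it expects.
- That the shares by visit cap the effect, or that only rollovers under 24 months at Day 1 are affected. Neither follows. The shares depend on the age mix and on when standing measurement starts. Protocol 9.1 also sets no maximum gap between the Study 122B follow-up visit and Day 1.
- That the BMI-for-age paragraph merely lacks a pointer to Appendix G. In fact 10.5.1 bases that z-score on unadjusted height, which disagrees with Appendix G for a child measured out of position for age.

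**Conclusion.** The concern holds, with a minor consequence. As written, the SAP subtracts a recumbent baseline from a standing follow-up for every child who switches, and no rule in it, Appendix G included, removes the difference.

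Per switching child, length/height change is understated by 0.7 cm, which rests only on the SAP's constant. BMI change is raised by about 0.2 to 0.3 kg/m² (0.22 to 0.34 over the assumed statures of 72–95 cm and BMI of 15–17, depending on the reference position).

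For a visit mean, the supportable range is 0 to 0.7 cm and 0 to about 0.3 kg/m². It cannot be narrowed, because the naïve/rollover split, the ages at entry and the age at which each child begins standing measurement are not given. The primary safety objective does not rest on these changes.

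**What to change.** 1. In SAP 10.5.1, keep the raw values and raw change that the protocol specifies. Add a supplementary change from baseline in length/height and BMI, with 95% CI and plot. Convert baseline and follow-up to one named stature basis using 0.7 cm, for children whose measuring position is recorded. Name the basis, because the BMI correction differs slightly between the two.
2. Report the number of children with unknown position. Show any version that uses the age default only as a sensitivity analysis.
3. Footnote the raw-change tables and plots in 10.5.1 and 10.6.4 to say that they mix measuring positions.
4. In the BMI-for-age z-score paragraph of 10.5.1, replace the reference to raw height with length/height adjusted per Appendix G, so that the two places agree for children measured out of position for age.

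Cost: one extra derivation with its table and plot, the footnotes, and one wording change. No new data are needed if the eCRF records position. The eCRF is not among the documents, so that has to be checked first. Protocol 9.1.6 also allows caregivers to measure stature at home, so position at those visits needs the same check.

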10.5.3 Absolute Change from Baseline in Fecal Calprotectin

Raw values and absolute change from baseline in fecal calprotectin levels at each visit will be summarized descriptively (n, mean, SD, SE, median, minimum, and maximum) based on the FAS. In addition, the 95% CI of the absolute change from baseline values will be provided. The mean (95% CI) of the absolute change from baseline in fecal calprotectin values will be plotted at each scheduled visit.

10.6 Safety Analysis

Evaluating the safety and tolerability of long-term LUM/IVA treatment is the primary objective of this study. The safety profile of the study drug will be assessed in terms of the following safety and tolerability endpoints:

- AEs
- Clinical laboratory measurements (serum chemistry and hematology)
- Standard 12-lead ECGs
- Vital signs
- Pulse oximetry
- Physical Examinations
- OEs

Safety endpoints will be summarized descriptively based on the Safety Set.

All listings will be provided based on the All Subjects Set.

10.6.1 Adverse Events

AEs will be classified as pretreatment AEs, treatment-emergent adverse events (TEAEs), or post-treatment AEs, defined as follows:

Pretreatment AE: Any AE that started before the first dose date of study drug in Study 124.

TEAE: Any AE that worsened (either in severity or seriousness) or that was newly developed on or after the first dose date of study drug through the end of the TE Period.

Post-treatment AE: Any AE that increased in severity or was newly developed after the TE Period.

For AEs with missing or partial start dates, if there is no clear evidence that the AEs started before or after study treatment, the AEs will be classified as TEAEs.

Details for imputing missing or partial start dates of AEs are described in Appendix.

TEAE summaries will be presented using number and percentages of subjects for the TE Period based on the Safety Set.

An overview of the TEAE profile will be provided, including total number of TEAEs, with number and percentage of subjects and for the following categories: (1) Any TEAEs; (2) Grade 3/4 TEAEs; (3) TEAEs by Strongest Relationship to the Drug; (4) TEAEs by Maximum Severity; (5) TEAEs Leading to Treatment Interruption; (6) TEAEs Leading to Treatment Discontinuation; (7) Serious TEAEs; (8) Related Serious TEAEs; (9) TEAEs Leading to Death.

AE summary tables will be presented for TEAEs only and will include the following:

- All TEAEs
- Grades 3/4 TEAEs
- TEAEs by Strongest Relationship
- TEAEs by Maximum Severity
- Related TEAEs
- TEAEs Leading to Treatment Interruption
- TEAEs Leading to Treatment Discontinuation
- Serious TEAEs
- Related Serious TEAEs
- TEAEs Leading to Death
- Frequently Reported TEAEs (≥5% at the PT level)

These summaries will be presented by MedDRA SOC and PT using frequency counts and percentages (i.e., number and percentage of subjects with any event) and exposure-adjusted number of events in 100PY. When summarizing the number of events, a subject with multiple events within a category is counted multiple times in that category. When

summarizing the number and percentage of subjects with any event, subjects with multiple occurrences of the same AE or a continuing AE will be counted once, only the maximum severity level will be presented in the severity summaries, and only the strongest relationship level will be presented in the relationship summaries.

Additional summary table in which the frequency counts and percentages will be presented for TEAEs during the TE period for the following:

- All TEAEs by PT
- Non-Serious TEAEs by SOC and PT
- Related Non-Serious TEAEs by SOC and PT

In addition, listings containing individual subject data for all TEAEs leading to treatment interruption, TEAEs leading to treatment discontinuation, deaths, and serious adverse events (SAEs) will be provided separately for the TE Period. All AEs, including pre- and post-treatment AEs, will be presented in individual subject data listings for the TE Period.

Note that if an event increases in its severity, it will be reported as a separate event in the clinical database and thus may be counted more than once.

Analysis of AEs of Special Interest (AESI):

Three types of AESIs are proposed for Study 124; the Customized MedDRA Queries (CMQ) used may change before database lock.

1. Elevated Transaminases AESI

The AESI of elevated transaminases is defined as AEs whose PTs fall into any of the following categories:

- Alanine aminotransferase abnormal
- Alanine aminotransferase increased
- Aspartate aminotransferase abnormal
- Aspartate aminotransferase increased
- Transaminases abnormal
- Transaminases increased
- Liver function test abnormal
- Liver function test increased
- Hypertransaminasaemia
- Hepatic enzyme increased
- Hepatic enzyme abnormal
- 2. Respiratory Symptom AESI

The AESI of respiratory symptoms is defined as AEs whose PTs fall into any of the following categories:

- Chest discomfort
- Dyspnoea
- Respiration abnormal
- 3. Respiratory Event AESI (including respiratory symptoms or reactive airways)

The AESI of respiratory symptoms or reactive airways is defined as AEs whose PTs fall into any of the following categories:

- Asthma
- Bronchial hyperreactivity
- Bronchospasm
- Chest Discomfort
- Dyspnoea
- Respiration abnormal
- Wheezing

TE AESIs will be summarized using the Safety Set by:

- 1. Number and percentage of subjects by PT
- 2. Number and percentage of subjects by Maximum Severity
- 3. Descriptive summary of duration of events (days)
- 4. Descriptive summary of time-to-onset of the first event (days, relative to first dose date)
- 5. Number and percentage of subjects with exposure-adjusted number of events in 100PY for: (1) TEAEs Leading to Treatment Interruption; (2) TEAEs Leading to Treatment Discontinuation; (3) Serious TEAEs; (4) Related Serious TEAEs; and (5) TEAEs Leading to Death

